9.2.2 Adverse Event Overview

The number and percentage of subjects experiencing TEAEs will be summarized by treatment group as specified in Section [6.0](#) and overall.

An overview of AEs will be presented consisting of the number and percentage of subjects experiencing at least one event for each of the following AE categories:

- Any treatment-emergent AE
- Any treatment-emergent AE related to study drug according to the investigator
- Any severe treatment-emergent AE
- Any serious treatment-emergent AE
- Any treatment-emergent AE leading to discontinuation of study drug

- Any treatment-emergent AE leading to death
- TEAE of special interest (AESIs) (as defined in [Appendix B](#))
- Any COVID-19 related AE
- All deaths
- COVID-19 related deaths

Additional AEs may be considered for tabulation/summary based on recommendations from Clinical and Safety as deemed appropriate.

The number and percentage of subjects experiencing at least one event of treatment-emergent AEs will be summarized for each treatment group. In addition, an overview of AEs per 100 patient-years of study exposure will be presented for the AE categories defined above. The number of TEAEs reported, the total number of years of study drug exposure, and the TEAE rate per 100 patient-years will be presented.

9.2.3 Treatment-Emergent Adverse Events by SOC and/or PT

Treatment-emergent adverse events will be summarized by SOC and PT; by maximum relationship to study drug as assessed by the investigator (e.g., reasonable possibility or no reasonable possibility) and SOC and PT; by maximum toxicity grade and SOC and PT; and by subject number and SOC and PT. Specific adverse events will be counted once for each subject for calculating percentages, unless stated otherwise. In addition, if the same adverse event occurs multiple times within a subject, the maximum toxicity grade and level of relationship to investigational product will be reported.

In addition, treatment-emergent adverse events will be summarized by PT and sorted by decreasing frequency for the total active group.

9.2.4 Treatment-Emergent Adverse Events per Patient-Years of Exposure

TEAEs occurring during Study M20-186 will be summarized by event rate per 100 subject years, defined as

$$100 * (\text{Number of TEAEs}) / (\text{Total Patient Years})$$

where total patient years is defined as the sum of the study drug exposure of all subjects normalized by 365.25 and rounded to 1 decimal place.

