Such an event can result from use of the drug as stipulated in the protocol, as well as from accidental or intentional overdose, drug abuse, or drug withdrawal. Any worsening of a pre-existing condition or illness is considered an AE. Worsening in severity of a reported AE should be reported as a new AE. Laboratory abnormalities and changes in vital signs are considered to be AEs only if they result in discontinuation from the study, necessitate therapeutic medical intervention, meet protocol-specific criteria (see Section 6.2 regarding toxicity management), and/or if the investigator considers them to be AEs. Worsening SLE including flares will be captured and analyzed via the disease activity forms (SLEDAI, BILAG, CLASI, and SFI) and will be analyzed as part of efficacy. As such, worsening SLE and flares will not be captured as AEs unless they result in serious outcomes.

The investigators will monitor each subject for clinical and laboratory evidence of AE on a routine basis throughout the study. All AEs will be followed to a satisfactory conclusion.

An elective surgery/procedure scheduled to occur during a study will not be considered an AE if the surgery/procedure is being performed for a pre-existing condition and the surgery/procedure has been pre-planned prior to study entry. However, if the pre-existing condition deteriorates unexpectedly during the study (e.g., surgery performed earlier than planned), then the deterioration of the condition for which the elective surgery/procedure is being done will be considered an AE. If the subject undergoes elective surgery, the study drug should be interrupted at least 1 week prior to the planned surgery. If the subject must undergo emergency surgery, the study drug should be interrupted at the time of the surgery. For both elective and emergency surgery, allow reintroduction of study drug once the physician has examined the surgical site and determined that it has healed and there is no sign of infection.

If any of the following events (Table 3) are reported, then the following supplemental report must be completed.

Table 3. Adverse Events Requiring Supplemental Reports

| Adverse Events | Supplemental Report |
|----------------------|---|

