9.2 Adverse Events

Adverse events (AEs) will be summarized and presented using primary MedDRA System Organ Classes (SOCs) and preferred terms (PTs) according to the version of the MedDRA coding dictionary used for the study at the time of database lock. The actual version of the MedDRA coding dictionary used will be noted in the AE tables and in the clinical study report. Specific adverse events will be counted once for each subject for calculating percentages, unless stated otherwise. In addition, if the same adverse event occurs multiple times within a subject, the maximum toxicity grade and level of relationship to investigational product will be reported.

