9.2.1 Treatment-Emergent Adverse Events

To summarize data from Study M20-186, a treatment-emergent Adverse Event (TEAE) is defined as an adverse event with an onset date that is on or after the first dose of study drug from Study M20-186, and no more than 30 days after the last dose of study drug from Study M20-186.

Events where the onset date is the same as Study M20-186 study drug start date are assumed to be treatment-emergent, unless the Study M20-186 study drug start time and the adverse event start time are collected and the adverse event start time is prior to the Study M20-186 study drug start time. If an incomplete onset date was collected for an adverse event, the event will be assumed to be treatment-emergent unless there is other evidence that confirms that the event was not treatment-emergent (e.g., the event end date was prior to the study drug start date). All treatment-emergent AEs will be summarized overall, as well as by primary MedDRA SOC and Preferred Term. The SOCs will be presented in alphabetical order, and the PTs will be presented in alphabetical order within each SOC.

The number and percentage of subjects experiencing TEAEs will be summarized.

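### AE event rates per 100 patient-years can count one worsening episode more than once, and the SAP has no exposure-adjusted measure that avoids this

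*SAP*

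**What the plan says.** Recording. Protocol 6.1 (Complaints and Adverse Events) states: "Worsening in severity of a reported AE should be reported as a new AE".

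Classification. SAP 9.2.1 defines a TEAE as "an adverse event with an onset date that is on or after the first dose of study drug from Study M20-186", with an upper limit of 30 days after the last M20-186 dose. A worsening entered with its own onset date in that window is thus a separate TEAE.

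Counting. SAP 9.2.2 states for the overview categories: "The number of TEAEs reported, the total number of years of study drug exposure, and the TEAE rate per 100 patient-years will be presented". SAP 9.2.4 states: "TEAEs occurring during Study M20-186 will be summarized by event rate per 100 subject years". The formula it gives is 100 times the number of TEAEs over total patient-years. For the denominator it adds: "total patient years is defined as the sum of the study drug exposure of all subjects normalized by 365.25 and rounded to 1 decimal place".

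Repeats. SAP 9.2, repeated in 9.2.3, has two rules. The first is "Specific adverse events will be counted once for each subject for calculating percentages, unless stated otherwise", which is limited to percentages. The second is "if the same adverse event occurs multiple times within a subject, the maximum toxicity grade and level of relationship to investigational product will be reported", which settles the grade and relationship shown for a repeated event, not how many events enter a rate.

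**The concern.** Longer-term safety is the primary objective. Protocol 4.2 sets the main comparison against the safety profile of each group in M19-130, which treated subjects for 48 weeks against 56 here. SAP 2.3 also allows whole treatment groups to be stopped early. With follow-up that can differ this much, crude subject percentages are hard to compare, and a reader will turn to the rates per 100 patient-years. The reported-event rate is the only exposure-adjusted AE summary in the SAP.

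That rate depends on how often sites enter a further report as an AE worsens. Two groups with the same number of episodes could show different rates if episodes in one more often rise in grade. SAP 13.0 adds that integrated data will be summarized later for the Phase 3 submission, so an unstated counting unit could also carry forward into that work.

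**Working it through.** **1. The plan's own figure.** The documents give no expected AE rate. The one related figure is enrolment. Protocol 4.1 projects 5 groups of 65: 5 × 65 = 325; 0.60 × 325 = 195 and 0.80 × 325 = 260, matching Protocol 7.7 and SAP 2.4. With everyone treated for the full 56 weeks (392 days), the denominator is 195 × 392 / 365.25 = 209.3 patient-years, or 260 × 392 / 365.25 = 279.0. Early discontinuation would lower both.

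**2. One episode.** Take a subject with 392 days of exposure, 392 / 365.25 = 1.0732 patient-years (unrounded), and a single episode rising from Grade 1 to 2 to 3, all reports starting in the window:

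- counted as one event: 100 × 1 / 1.0732 = 93.2 per 100 patient-years
- counted as two reports: 100 × 2 / 1.0732 = 186.4
- counted as three reports: 100 × 3 / 1.0732 = 279.5

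Exposure does not change with the number of reports, so the rate rises in proportion. The subject percentage is the same in all three cases.

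**3. Study level.** Let *w* be the share of in-window episodes that worsen and *k* the extra reports for each of these. Then

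reported rate = episode rate × (1 + *w* × *k*).

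Both inputs are assumptions, as is an episode rate of 200 per 100 patient-years:

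| *w* | *k* | Factor | Reported rate |
|---|---|---|---|
| 2% | 1 | 1.02 | 204 |
| 5% | 1 | 1.05 | 210 |
| 10% | 1 | 1.10 | 220 |
| 20% | 1 | 1.20 | 240 |
| 20% | 2 | 1.40 | 280 |

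The factor depends on neither enrolment nor the assumed episode rate. At 300 episodes per 100 patient-years the first and last rows become 306 and 420.

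**4. Which results are exposed.**

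- Any TEAE, and AESIs found by MedDRA query: exposed whenever both reports fall in the window.
- Severe TEAEs: a rise from Grade 1 to 3 counts once. A rise from Grade 3 to 4 counts twice, because Protocol 6.1 puts Grades 3 to 5 under severe.
- SAEs and AEs leading to discontinuation: counted twice only if both reports carry the flag.
- MACE, VTE and GI perforation: taken from adjudication (SAP Appendix B), so largely unaffected.
- Deaths and all subject percentages: not affected.
- An AE that began in M19-130 and worsened once in the extension: only the worsened report is in the window, so it counts once.

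**5. A measure without the problem.** For subjects with a first event per 100 patient-years at risk, each subject adds at most one event and time at risk stops at its onset. Later reports of the same episode change neither numerator nor denominator.

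**The case against.** The strongest reply is that the plan is consistent with itself. The protocol treats a worsening as a new AE, Protocol 7.4 includes worsening in its TEAE definition, and the SAP counts TEAEs and calls the result an event rate. Nothing commits the sponsor to an episode-based rate. This stands: the reported-event rate is a legitimate quantity and should not be called wrong.

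The scope is also narrow. The protocol says a worsening should be reported anew, not that it must be. Under Protocol 6.1 a laboratory abnormality is an AE only under stated conditions, so a change of grade alone need not create a report. SLE worsening and flares are kept out of AE reporting unless the outcome is serious. All of this stands and limits the effect.

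Merging reports in place of counting them could harm the main comparison. If M19-130 counted reports, merging only in the extension would lower its rates artificially. The M19-130 convention is not in these documents, so the reported-event rate should be kept.

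Subject percentages and listings are planned too. They help only in part: percentages ignore unequal follow-up, and listings are not a summary measure. The Operations Manual, whose text is not among the documents reviewed, might contain linking instructions; the counting unit still belongs in the SAP.

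A reader might infer that comparisons between groups are biased. Upadacitinib's potential risks in Protocol 2.2 include graded conditions such as cytopenias, and exposure to it differs by group, so unequal inflation is possible. The documents do not show that it will occur: one recording rule applies to every group and sites stay blinded.

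**Conclusion.** The point holds with limits. On the plain reading of Protocol 6.1 with SAP 9.2.1, 9.2.2 and 9.2.4, an episode with two or more reports starting in the M20-186 window counts two or more times in the event rates. The main effect is on all-TEAE rates and non-adjudicated AESIs.

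Its size cannot be taken from the documents. The factors of 1.02 to 1.40 rest on assumed shares of worsening episodes (2% to 20%) and one or two extra reports each; they show sensitivity and do not forecast. A reader might infer that the planned rates are too high by some such percentage, or that the study's safety results as a whole are inflated. Neither follows: the first presumes an episode-based target that the plan never adopts, and the second overlooks the unaffected percentages and deaths and the largely unaffected adjudicated events.

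This is a worthwhile, cheap improvement. The reason to act is that the only exposure-adjusted measure for the primary objective depends on how AE reports are split.

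**What to change.** In SAP 9.2.2 and 9.2.4:

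1. Keep the reported-event rate and label it as counting AE reports, including worsenings entered as new AEs. It can then be set beside M19-130 if that study counted the same way.
2. Add, for any TEAE, SAEs, AEs leading to discontinuation and each AESI, the number of subjects with a first event per 100 patient-years at risk, with time censored at the first event. State where time at risk ends for subjects without the event.
3. As a sensitivity rate, count contiguous M20-186 TEAE reports of the same preferred term in the same subject as one episode at maximum grade. Contiguous means that onset is no later than the day after the previous report ends. Carry over any serious, related or discontinuation flag. Merge only reports already classed as M20-186 TEAEs, so that a worsening of an M19-130 event still counts.

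The cost is a few lines of SAP text, one programming step and a few extra tables, from data already collected. In the sensitivity rate, true back-to-back or concurrent episodes of one term, or reports with a missing end date, may be merged; the SAP should say how missing end dates are handled.

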Important Medical Event Requiring Medical or Surgical Intervention to Prevent Serious Outcome An important medical event that may not be immediately life-threatening or result in death or hospitalization, but based on medical judgment may jeopardize the subject and may require medical or surgical intervention to prevent any of the outcomes listed above (i.e., death of subject, life-threatening, hospitalization, prolongation of hospitalization, congenital anomaly, or persistent or significant disability/incapacity). Additionally, any elective or spontaneous abortion or stillbirth is considered an important medical event. Examples of such events include allergic bronchospasm requiring intensive treatment in an emergency room or at home, blood dyscrasias or convulsions that do not result in inpatient hospitalization, or the development of drug dependency or drug abuse.

Adverse Event Collection

All AEs reported from the time of study drug administration until 30 days after discontinuation of study drug administration will be collected, whether solicited or spontaneously reported by the subject.

The following definitions will be used for Serious Adverse Reactions (SAR) and Suspected Unexpected Serious Adverse Reaction (SUSAR):

SAR

Defined as all noxious and unintended responses to an Investigational Medicinal Product (IMP) related to any dose administered that result in death, are life-threatening, require inpatient hospitalization or prolongation of existing hospitalization, result in persistent or significant disability or incapacity, or are a congenital anomaly or birth defect.

SUSAR

A suspected unexpected SAR: refers to individual SAE case reports from clinical trials where a causal relationship between the SAE and the IMP was suspected by either the sponsor or the investigator, is not listed is the applicable Reference Safety Information (RSI), and meets one of the following serious criteria: results in death, is life-threatening, requires hospitalization or prolongation of an existing hospitalization, results in persistent or significant disability or incapacity, or is a congenital anomaly or birth defect.

AbbVie will be responsible for SUSAR reporting for the IMP in accordance with global and local requirements.

Adverse events will be monitored throughout the study to identify any of special interest that may indicate a trend or risk to subjects.

Adverse Events of Special Interest

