2.3 Treatment Assignment and Blinding

Prior to the planned Study M19-130 Interim Analysis, qualified subjects entering into LTE Study M20-186 stayed in their original treatment group from Study M19-130 if on

an ABBV-599 (elsubrutinib/upadacitinib) combination, elsubrutinib 60 mg monotherapy, or upadacitinib 30 mg monotherapy. Those originally assigned to the placebo group in Study M19-130 were randomized centrally in a 1:1 ratio to the 2 ABBV-599 (elsubrutinib/upadacitinib) combination treatment groups.

Prior to the planned Study M19-130 Interim Analysis, there were 4 treatment groups in this LTE study:

- Group 1: Elsubrutinib 60 mg QD and upadacitinib 30 mg QD
- Group 2: Elsubrutinib 60 mg QD and upadacitinib 15 mg QD
- Group 3: Elsubrutinib 60 mg QD and upadacitinib placebo QD
- Group 4: Elsubrutinib placebo QD and upadacitinib 30 mg QD

A planned unblinded interim analysis for Study M19-130 was performed when 50% of the planned subjects completed their Week 24 assessments. The objective of this analysis was to reassess the treatment regimens in Study M19-130 and the benefit/risk for rollover into Study M20-186.

Based on the benefit/risk assessment of the planned Study M19-130 Interim Analysis, subjects in 1 or more groups of LTE Study M20-186 may be discontinued. Subjects in any discontinued group(s) should return for a Premature Discontinuation (PD) visit and have a follow-up phone call 30 days after the last study drug dose.

This study includes a 56-week double-blind treatment period with study visits conducted at Weeks 48, 56, 64, 72, 80, 88, 96, and 104 (from the Baseline visit of Study M19-130), and a subsequent telephone follow-up call 30 days after the last visit to determine the status of any ongoing AEs/SAEs or the occurrence of any new AEs/SAEs. The plan is to extend the trial if data support the safety and efficacy endpoints during the 56-week LTE study duration.

The M19-130 Primary Analysis will be performed when all subjects have completed the Week 24 visit. The M20-186 study team will become unblinded after the M19-130

Week 24 Primary Analysis has been completed. Study sites and subjects will remain blinded to treatment assignment in Study M19-130 and Study M20-186 throughout the studies.

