6.0 Study Drug Duration and Compliance

Study Drug Duration

A summary of study drug duration (days) will be provided by each treatment arm for the Safety Analysis Set.

The duration of exposure to study drug will be summarized for each group as specified in Section 5.0, with the number of subjects, mean, standard deviation, median, minimum and maximum values. In addition, the number and percentage of subjects exposed to study drug will be summarized for Study M20-186 treatment period based on the following duration intervals:

- ≥ 1 day

- ≥ 57 days
- ≥ 113 days
- ≥ 169 days
- ≥ 225 days
- ≥ 281 days
- ≥ 337 days
- ≥ 393 days

The exposure to study drug in days for Study M20-186 period is calculated as:

Exposure = (date of last study medication in Study M20-186 – date of first study medication in Study M20-186 + 1)

Compliance

Study drug compliance will be summarized for each treatment group for FAS population. Descriptive statistics will be provided including sample size, mean, standard deviation, median, minimum and maximum.

Treatment compliance (TC) will be calculated using the following formula:

$$TC = \frac{\text{Total number of tablets/capsules taken}}{(last \ dose \ date - first \ dose \ date + 1) \times <\text{number of tablets/capsules per day}>} \times 100\%$$

- The total number of tablets/capsules taken will be calculated as the total number of tablets/capsules dispensed minus the total number of tablets/capsules returned.
Note: If the bottle is not returned, total number of tablets/capsules returned is assumed to be 0.
- In M20-186: number of tablets per day is 1 and number of capsules per day is 3.

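### TEAE rates per 100 patient-years count events to 30 days after the last dose but stop the patient-years at the last dose; matched-window rates should be shown beside them

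*SAP*

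**What the plan says.** **Numerator.** SAP 9.2.1 treats an event as a TEAE if its onset is on or after the first M20-186 dose and "no more than 30 days after the last dose of study drug from Study M20-186". SAP 9.2.4 puts all TEAEs into the rate.

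**Denominator.** SAP 9.2.4: "total patient years is defined as the sum of the study drug exposure of all subjects normalized by 365.25". Under SAP 6.0 a subject's exposure ends at the "date of last study medication in Study M20-186"; it is that date minus the first-dose date, plus 1. Nothing is added for follow-up.

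**Labels.** SAP 9.2.2 promises "an overview of AEs per 100 patient-years of study exposure", and the next sentence says that the table will show "the total number of years of study drug exposure". Protocol 7.4 asks for events per 100 patient-years without defining patient-years.

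**Follow-up of the tail.** Protocol 6.1: "All AEs reported from the time of study drug administration until 30 days after discontinuation of study drug administration will be collected". SAP 2.3 says that "subjects in 1 or more groups of LTE Study M20-186 may be discontinued", and that such subjects should "have a follow-up phone call 30 days after the last study drug dose".

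No section limits the rate numerator to events up to the last dose, and none extends patient-years into the 30-day window.

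**The concern.** A rate per unit of time should count events over the same time that it divides by. Here up to 30 days per subject can contribute events but never time. If any event falls in that tail, the printed rate exceeds the rate from first to last dose. The excess is larger the shorter the exposure.

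Longer-term safety is the primary objective. SAP 9.2.2 applies the rate to its whole list of overview categories, including serious, severe and special-interest events. Whole groups may be stopped early, so mean exposure may differ between groups. Two groups with the same underlying rate could then show different printed rates.

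**Working it through.** **Inputs from the documents**
- Tail: 30 days (SAP 9.2.1).
- Planned course: Week 48 to Week 104, so 56 × 7 = 392 days (SAP 2.3).
- Feeder study: 5 groups × 65 = 325 (Protocol 4.1). 60% is 195 and 80% is 260, which reproduces the enrolment range in SAP 2.4.

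The documents state no TEAE rate and no patient-year total, so there is no planned rate to reproduce.

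**Assumptions (not in the documents)**
- h, the event rate in the tail relative to the rate between first and last dose: 0 to 1. This is an illustration, not a bound; h above 1 would enlarge the excess.
- Mean exposures of 281, 225 and 169 days, taken from the SAP 6.0 duration cut-points to represent groups stopped early.
- A constant rate from first to last dose, and a full 30-day tail for every subject.

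**Formulas**, with E = mean days from first to last dose
- Excess of the SAP rate over the first-to-last-dose rate: h × 30/E.
- Ratio of a shorter group to a 392-day group at the same underlying rate: (1 + 30h/E) / (1 + 30h/392).
- All TEAEs over the full window (E + 30 days), relative to the first-to-last-dose rate: 30(h − 1)/(E + 30).

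| E (days) | SAP excess, h = 0 / 0.5 / 1 | Ratio to full course, h = 0.5 / 1 | Full-window rate, h = 0 / 0.5 / 1 |
|---|---|---|---|
| 392 | 0 / 3.8% / 7.7% | 1 / 1 | −7.1% / −3.6% / 0 |
| 281 | 0 / 5.3% / 10.7% | 1.01 / 1.03 | −9.6% / −4.8% / 0 |
| 225 | 0 / 6.7% / 13.3% | 1.03 / 1.05 | −11.8% / −5.9% / 0 |
| 169 | 0 / 8.9% / 17.8% | 1.05 / 1.09 | −15.1% / −7.5% / 0 |

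For example, at 169 days with h = 1: 30/169 = 17.8%, and 1.178/1.077 = 1.09.

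**Which is closer to the first-to-last-dose rate?** The SAP rate and the full-window rate are equally far from it when h = E/(2E + 30): 392/814 = 0.48 at 392 days and 169/368 = 0.46 at 169 days. Below that h the SAP rate is the closer of the two.

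**Against random error, one group, full course.** With equal rollover assumed, 60% to 80% of 65 is 39 to 52 subjects in each of Groups 1 to 4.
- Patient-years: 39 × 392/365.25 = 41.9; 52 × 392/365.25 = 55.8.
- At an assumed 200 events per 100 patient-years: 84 to 112 events. The Poisson standard error is 1/√83.7 = 10.9% to 1/√111.6 = 9.5%.
- Extra tail events at h = 1: 39 × 30/365.25 × 2 = 6.4; 52 × 30/365.25 × 2 = 8.5.

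The largest excess, 7.7%, is below one standard error in a single group. That would not hold for all groups pooled: 195 × 392/365.25 × 2 = 419 events, with a standard error of 1/√419 = 4.9%.

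**The case against.** The strongest reply is that the SAP specifies its rate in full. The heading and formula of 9.2.4 say that it is per patient-years of exposure, and 9.2.2 prints the event count, the exposure and the rate together. A stated convention is not a contradiction, and the documents never make a first-to-last-dose rate the target. This stands as far as it goes, and it is why the current rate need not be replaced. But a reader of the tables cannot take the tail out. Tail events are not counted separately, and the SAP 9.2.9 listings cover special-interest events, serious events, discontinuations and deaths rather than all TEAEs.

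The alternatives also have limits. SAP 6.0 exposure does not deduct the dosing interruptions that Protocol 6.1 and 6.2 provide for, so events up to the last dose over that exposure are not a pure on-drug rate. Splitting events at the last dose needs a rule for incomplete onset dates, because 9.2.1 decides only whether such events are treatment-emergent. Follow-up of the tail may be incomplete: for subjects who withdraw consent, Protocol 5.6 makes the 30-day call optional. All of this stands and shapes the fix.

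A reader might infer more: that early-stopped groups will look worse, or that the comparison with Study M19-130, which Protocol 4.2 makes primary, is biased. The documents do not support either. They do not say which groups stop or when, they give no tail event rate, and they do not state the rate convention used in M19-130. If the conventions match, a new leading rate could itself harm comparability.

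**Conclusion.** The mismatch holds and no section reconciles it; its existence is certain from SAP 6.0, 9.2.1 and 9.2.4. Its size is not certain, because it depends on the tail event rate and on the exposure distribution. For h between 0 and 1 it is modest at full course and grows as exposure shortens. If no tail events occur, there is no excess.

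No hypothesis test is planned and subject percentages are unaffected. The effect on the comparison with M19-130 is unknown. Severity: minor.

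**What to change.** In SAP 9.2.2 and 9.2.4:

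1. Call the denominator *study drug exposure* throughout.
2. Keep the current rate, with a footnote that events are counted to 30 days after the last dose while time stops at the last dose. This keeps it available for comparison with M19-130 and for the later integrated summary noted in SAP 13.0.
3. Beside it, for the 9.2.2 categories, add matched-window rates:
   - (a) TEAEs with onset from first to last M20-186 dose, over SAP 6.0 exposure. Label it a first-to-last-dose rate, because interruptions are not deducted. Count an incomplete onset date as on or before the last dose unless other evidence shows a later onset.
   - (b) All TEAEs, over time from first dose to the earliest of last dose + 30 days, death, end of participation or data cut-off. Label it as the rate over the TEAE window.

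The cost is one or two extra derived rates from data already collected, a date rule, and some SAP wording. Rate (a) leaves out post-dose events, which remain in the TEAE percentages (SAP 9.2.2 and 9.2.3). Rate (b) lies below the first-to-last-dose rate when h is below 1. Neither needs to replace the current rate as the leading figure.
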